## Research Question and Hypothesis

We hypothesize that reducing the burden of anxiety symptoms using Acceptance and Commitment Therapy (ACT) will improve vascular function, inflammation, mSNA, and oxidant stress. If our hypothesis is correct, then we predict that: 1) Vascular function, inflammation, muscle sympathetic nerve activity (mSNA), and oxidant stress will be elevated in individuals with anxiety compared to those with low or no anxiety, 2) ACT will improve forearm blood flow during reactive hyperemia; 3) ACT will decrease mSNA; 4) ACT will improve microvascular, including retinal vascular, and large elastic artery function per pulse wave velocity (PWV) measurements and 5) ACT will improve autonomic function measured by 24-hour blood pressure variability and heart rate variability measures. We will also be able to explore other secondary endpoints related to oxidant stress and inflammation in vascular endothelial cells. If anxiety increases inflammation, then we predict that ACT will reduce circulating pro-inflammatory cytokines, and produce a phenotype of endothelial cell proteins reflecting decreased inflammation compared to pre-treatment. And if anxiety increases oxidative stress, then we predict that ACT will produce a phenotype of endothelial cell proteins reflecting decreased oxidant stress and increased nitric oxide synthase activity.

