## Description of Study Population

We will enroll 150 healthy men and women age 25-65 years who are experiencing feelings of anxiety based on the online pre-screen survey.

Inclusion Criteria:

- Willing and able to provide written, signed consent after the nature of the study has been explained, and prior to any research-related procedures.
- Age is  $>$  or  $=$  25 and  $<$  or  $=$  65 years of age.
- Healthy, as determined by health history questionnaire, blood chemistries, and 12-lead ECG.
- Blood chemistries indicative of normal renal (creatinine  $<$ 2.0mg/dl), liver ( $<$ 3 times upper limit for ALT, AST), and thyroid function (TSH between 0.4 - 5.0 mU/L) or on stable thyroid medication with no dose change for 3 months.
- If currently receiving treatment with or taking any of the following supplements, must be willing and able to discontinue taking for 2 weeks prior to each study visit and/or throughout the treatment period: Vitamin C, E or other multivitamins containing vitamin C or E; omega-3 fatty acids; Phosphodiesterase (PDE) 5 inhibitors (i.e. Viagra®, Cialis®, Levitra®, or Revatio®); PDE 3 inhibitors (e.g., cilostazol (Pletal®), milrinone, or vesnarinone).
- No history of cardiovascular disease (e.g., heart attack, stroke, heart failure, valvular heart disease, cardiomyopathy), or peripheral arterial disease.
- Non-smokers, defined as no history of smoking or no smoking for at least the past 3 months.
- Normal resting 12-lead ECG (no evidence of myocardial infarction, left ventricular hypertrophy, left-bundle branch block, 2nd or 3rd degree AV block, atrial fibrillation/flutter, atherosclerosis).

Exclusion Criteria:

- Current diagnosis or history of cancer, liver disease, HIV/AIDS
- History of brain tumor, aneurysm or injury
- Clinical diagnosis of mental health disorders such as bipolar disorder or schizophrenia

- History of cardiovascular disease such as heart angioplasty/stent or bypass surgery, my lute with or without LV ejection fraction <40%, cardiomyopathy, valvular heart disease, cardiomyopathy, heart transplantation, atherosclerosis.
- Current tobacco user or history of tobacco use within the past 3 months (cigarettes, cigars, chewing tobacco, Hookah).
- History of lung emphysema, chronic bronchitis or chronic obstructive pulmonary disease (COPD).

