### Primary Endpoint Analysis

Changes in our primary outcome of interest, anxiety as measured by the Beck anxiety inventory (BAI), will be assessed using a linear mixed effect model with intervention group as the fixed effect between-subjects factor of interest and repeated measurements (baseline, 6 weeks, 12 weeks) within-subjects of the anxiety inventory as the primary dependent variable. Individual participants will be initially modeled as a random effect including both an intercept term and, if necessary, slope. The random effect for slope will be removed for an intercept only model if the random slope does not substantively improve the model or if there are issues with model fitting. Fixed effects covariates for any sociodemographic or clinical variables that differ between groups despite randomization can be added.

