### Secondary Endpoint Analysis

State and Trait subscales of the STAI will be secondarily modeled as the dependent variable to assess changes in the domains of trait and state anxiety.

The novel physiological variables (vascular function, mSNA, inflammation) will serve as secondary outcomes and will be explored in analogous to the above. We will also assess for any relationship between these variables and changes in anxiety across groups in linear regression models (since these physiological variables are only measured at two points, there is no need for linear mixed models). For these latter analyses, variables for relevant sociodemographic and clinical confounds will need to be included as change in anxiety is not assigned by randomization akin to group assignment. Comparisons between the groups of higher anxiety and low anxiety will be made using one-way analysis of variance to determine differences in vascular function, mSNA, and inflammation. Baseline values for the higher anxiety group will be compared to the values obtained from the low anxiety group during their one-time experimental visit.

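### The anxious versus low-anxiety comparison is not randomised but is tested by one-way ANOVA without covariates, so an age or sex difference between the groups can create or mask a result

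*Combined protocol and SAP*

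**What the plan says.** Under Research Question and Hypothesis, prediction 1 is that the listed physiological measures "will be elevated in individuals with anxiety compared to those with low or no anxiety". Secondary Endpoint Analysis gives the test: "Comparisons between the groups of higher anxiety and low anxiety will be made using one-way analysis of variance". It then gives the data: "Baseline values for the higher anxiety group will be compared to the values obtained from the low anxiety group during their one-time experimental visit".

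The plan mentions covariates in two other places:

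- Primary Endpoint Analysis, on the randomised arms: "Fixed effects covariates for any sociodemographic or clinical variables that differ between groups despite randomization can be added".
- Secondary Endpoint Analysis, on the regressions relating physiological variables to change in anxiety: "For these latter analyses, variables for relevant sociodemographic and clinical confounds will need to be included as change in anxiety is not assigned by randomization".

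Description of Study Population covers only the anxious participants: "We will enroll 150 healthy men and women age 25-65 years who are experiencing feelings of anxiety". The Randomization section allocates ACT versus control in a 2:1 ratio and nothing else.

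**The concern.** A one-way ANOVA compares raw group means. That is a fair comparison when randomisation forms the groups. Here one group is the trial sample at baseline and the other is a separate set of people selected for low anxiety. If the two sets differ in mean age or in the proportion of women, any outcome that varies with age or sex will differ between them even if anxiety has no effect. An imbalance in the other direction would hide a real difference.

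The plan recognises this problem for one non-randomised analysis and leaves it unaddressed in the next. At stake is the first listed prediction. It could appear supported, or fail, because of who was recruited into each group.

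**Working it through.** **Reading the text.** Could the confounder requirement already cover the ANOVA?

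1. The requirement is limited to the latter analyses, and its stated reason is that change in anxiety is not randomised. The sentence before it describes the regressions on change in anxiety. The low-anxiety group is seen once, so it has no change score.
2. The ANOVA sentence comes after the requirement, names a different method and lists no covariate.
3. The covariate option under Primary Endpoint Analysis is optional and concerns chance imbalance between randomised arms.
4. No section describes matching the low-anxiety group, or balancing it on age or sex.

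The comparison is therefore unadjusted as planned.

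**The plan's own figures.** Sample Size gives 38 per group, or 43 after 10% dropout. Both reproduce: 2(1.96 + 0.84)² × (1 + 2 × 0.4)/(3 × 0.5²) = 37.7 with unrounded normal quantiles, rounded up to 38; and 38/0.9 = 42.2, rounded up to 43. They apply to the repeated-measures comparison of ACT with control. No size or power is stated for the anxious versus low-anxiety comparison, so there is no figure to reproduce for this point.

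**Illustrating the size.** Inputs:

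- From the documents: 150 anxious participants; ages 25 to 65; α = 0.05, taken as two-sided.
- Assumed: 50 or 25 low-anxiety participants; ages uniform over the range, so SD = 40/√12 = 11.55 years; age-outcome correlation r of 0.3 to 0.7; mean age gaps of 0 to 5 years; no true difference.

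Formulas, with n₂ the size of the low-anxiety group:

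- Bias in outcome SD units: b = r × gap/11.55
- Standard error: se = √(1/150 + 1/n₂), which is 0.163 for n₂ = 50 and 0.216 for n₂ = 25
- False-positive rate: Φ(b/se − 1.96) + Φ(−b/se − 1.96)

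| Mean age gap | b (r = 0.3; 0.7) | Rate, 150 vs 50 | Rate, 150 vs 25 |
|---|---|---|---|
| 0 years | 0; 0 | 5% | 5% |
| 1 year | 0.026; 0.061 | 5.3%; 6.6% | 5.2%; 5.9% |
| 2 years | 0.052; 0.121 | 6.2%; 11.5% | 5.7%; 8.7% |
| 5 years | 0.130; 0.303 | 12.5%; 45.9% | 9.2%; 28.9% |

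Worked example (5 years, r = 0.7, 150 versus 50): b = 0.7 × 5/11.55 = 0.303; b/se = 1.856; Φ(−0.104) + Φ(−3.816) = 0.459.

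**Simulation check.** With 20,000 runs at 150 versus 50, the unadjusted rates were 6.2% and 11.6% at 2 years, and 12.1% and 44.8% at 5 years. With age in the model the rate was 4.8% to 5.2% at gaps of 0, 2 and 5 years.

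**Masking.** A 5-year gap in the opposite direction reduces a true difference of 0.5 SD, the effect size used in Sample Size, to 0.50 − 0.130 = 0.37 or 0.50 − 0.303 = 0.20 SD. A smaller true difference of 0.30 SD falls to 0.17 or 0.00 SD.

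**The case against.** The strongest case against the point concerns its weight, not its reading of the text.

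- **Importance.** The comparison is cross-sectional and secondary. The Purpose section does not mention it, no sample size is set for it, and its place at the head of the predictions does not make it a priority. This stands, and it limits the severity.
- **No imbalance is shown.** Bias arises only if the groups differ in age or sex, and the documents do not say that they do. If the trial's eligibility criteria also govern the low-anxiety group, they exclude smokers, cardiovascular disease, steroid use and autoimmune disease, which removes some confounding. This also stands. It still leaves a 40-year age range and both sexes without adjustment.
- **The numbers rest on assumptions.** Group size, age distribution, correlation and age gap are all assumed, and sex is not quantified. The simulation shows that adjustment works for the one confounder it contains, not that it removes all confounding. The 0.30 SD masking case nearly equals the largest assumed bias, so it is an extreme illustration; at the plan's own 0.5 SD the effect is attenuated, not erased. These points stand, and the figures should be read as a sensitivity range.
- **Other remedies exist.** Extending the plan's existing confounder sentence to this comparison, or matching the groups, would also answer the point. That is fair. Matching has to be arranged at recruitment, while adjustment needs only the covariate data.

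None of this supplies a reason to prefer the unadjusted ANOVA.

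**Conclusion.** The point holds. The plan names an unadjusted test for a non-randomised comparison, and its own reason for adjusting the neighbouring regressions applies equally here. Under the stated assumptions with 50 low-anxiety participants, a 1-year age gap does little harm (5% to 7% false positives per outcome), a 2-year gap gives 6% to 12%, and a 5-year gap gives 12.5% to 46%. With 25 low-anxiety participants the 5-year range is 9% to 29%. The actual bias cannot be determined from the documents and would be zero if the groups were balanced on age, sex and other confounders. This is an improvement the sponsor should make to a secondary, associational analysis. The randomised comparison on the Beck anxiety inventory does not depend on it.

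**What to change.** In Secondary Endpoint Analysis, replace the one-way ANOVA with a linear model (ANCOVA) of each outcome on anxiety group, adjusted for prespecified age and sex. Report the adjusted difference with its 95% confidence interval and describe it as a non-randomised association.

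Age and sex are safe covariates because anxiety cannot cause them. Put resting blood pressure and antidepressant or vasoactive medication use in one prespecified sensitivity model only: they may lie on the path from anxiety to vascular function, or closely track anxiety status.

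Record the same covariates at the low-anxiety group's single visit. Stating that group's eligibility criteria and planned number in the same edit would let a reader judge how comparable the groups are.

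The cost is a few lines of SAP text and two degrees of freedom in the main model. Age and sex must be available for the low-anxiety participants; the documents do not say whether they are recorded. The randomised analysis is unchanged.

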## Sample Size

Using the estimating equations of Diggle et al. (2002) and based on three assessments for primary and secondary outcomes and a correlation of outcome measures over the duration of the study within individuals of 0.4, a total of 38 participants are needed per group to detect an effect size of 0.5 SD with 80% power at an  $\alpha=0.05$  (as calculated in SAS 9.3 using relevant formula). Assuming an 10% dropout rate our sample size would need to be adjusted to  $38/(1-0.1)=43$  per group using the formula from Friedman et al. (2010). A 0.5 SD difference on the anxiety inventory should represent a clinically significant effect. A corresponding change of similar magnitude on the better studied Hamilton Depression Rating Scale (not used in this study) has been considered clinically significant (Hegerl et al. 2012). Similarly, we are powered to detect clinically significant effects for the secondary outcomes of vascular function. We will

assess large vessel measures (e.g. pulse wave velocity), resistance vessel measures (forearm blood flow), and microvascular measures in the retina. In a study of brachial artery flow-mediated dilation (FMD), a reduction in FMD of 0.66 SD was associated with a 30% increased risk of cardiovascular events (Shimbo D et al. 2007). Similar results were seen in another population-based study wherein each 0.66 standard deviation in FMD was associated with an 18% increased risk of composite cardiovascular events and 36% increase risk of myocardial infarction, resuscitated cardiac arrest or coronary heart disease death (Yeboah J et al. 2009). Thus, we should be powered to detect clinically significant changes in vascular function.

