## Randomization

A statistician will develop a computer program in R that will generate a 2:1 randomization for the ACT intervention group versus the control group, respectively.

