## Assessment Schedule

### Intervention Group

- 1) Visit 1: Consent and Screening
  - a) Explanation of the study; reading and signing of written informed consent document
  - b) If subject consents, but requires a 2 week washout for vitamins or supplements, aspirin, NSAIDs, PDE-5 or PDE-3 inhibitors, Visit 2 will not be scheduled for 2 weeks post-Visit 1 completion.
  - c) If subject consents and no washout is needed, screening tests will be performed on the same day to determine further eligibility by the following:
    - i) Research staff will obtain resting vitals (heart rate, blood pressure) and resting 12 lead ECG.
    - ii) -Subject will fill out the Demographics Document, Health History Survey (including current medications), Sleep Surveys (including the Berlin Questionnaire, Karolinska Sleep log and the Sleep Quality Assessment [PSQI]) and Modified Activity Questionnaire. The following questionnaires will be completed online: State-Trait Anxiety Inventory, Positive and Negative Affect Schedule-Expanded Form, Anxiety Inventory, Depression Inventory, Early Experience Questionnaire, Acceptance and Action Questionnaire II, Committed Action Questionnaire, Short Form Health Survey.
    - iii) -Research nurse or trained staff will obtain venous blood draw (1/2 teaspoon) using butterfly needle for UIHC pathology labs: TSH only.
  - d) Subject will meet with a physician or other trained interviewer who will ask detailed questions about their medical history, structured psychiatric history (MINI) and

medication use. The subject may skip or refuse to discuss any questions/topics they wish not to answer. To minimize participant burden and accommodate participant schedules, visit procedures may be split across multiple days.

- e) Subject will undergo visual acuity, intraocular pressure test as well as a blood pressure measurement. The subject will then undergo ocular coherence tomography and laser-speckle blood flow imaging. As with microneurography (Visit 2), two E4 wristbands (one on each wrist) will be worn and a mental math test and a cold pressor test may also be performed during laser-speckle blood flow imaging.
- 2) Visit 2: Pre-Intervention Visit
- a) Subject will arrive at the CRU between 7-9 am after an overnight 8 hour fast (water encouraged).
    - i) Subjects on vasoactive medications will be asked to hold medications on the morning of experimental testing, but will bring medications with them to be taken after the visit.

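### The 38 (43 with dropout) per group for 80% power belongs to a different design: one of the three BAI assessments is baseline, allocation is 2:1, 150 are enrolled, and no power is stated for that trial

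*Combined protocol and SAP*

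**What the plan says.** Sample Size states that "a total of 38 participants are needed per group to detect an effect size of 0.5 SD with 80% power", at alpha 0.05, with a within-person correlation of 0.4 and "based on three assessments for primary and secondary outcomes". Dividing by 0.9 for 10% dropout gives 43 per group. The section then adds: "Similarly, we are powered to detect clinically significant effects for the secondary outcomes of vascular function", and lists pulse wave velocity (PWV), forearm blood flow and retinal measures.

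The design is described elsewhere:

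- Primary Endpoint Analysis uses a linear mixed model with "repeated measurements (baseline, 6 weeks, 12 weeks) within-subjects of the anxiety inventory as the primary dependent variable". Group is the fixed effect of interest. No time point, group-by-time term or contrast is named.
- Randomization will "generate a 2:1 randomization for the ACT intervention group versus the control group".
- Description of Study Population: "We will enroll 150 healthy men and women age 25-65 years who are experiencing feelings of anxiety".
- Under Assessment Schedule, consent comes first and then "screening tests will be performed on the same day to determine further eligibility". The anxiety inventory is completed at Visit 1 ("Positive and Negative Affect Schedule-Expanded Form, Anxiety Inventory, Depression Inventory") and again at Visit 2, both before the workshop.
- PWV is measured at Visits 2 and 4. Forearm flow and muscle sympathetic nerve activity (mSNA) are measured at Visit 2, week 6 and Visit 4. Retinal imaging appears at Visit 1 only, and Visit 4 repeats Visit 2.

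**The concern.** A formula that averages a 0.5 SD difference over three assessments does not fit a trial in which one of the three precedes treatment. Randomisation makes the expected difference at that assessment zero. With 2:1 allocation there is also no common number per group, and no step in the documents leads from 43 per group (86 in total) to 150. The reader therefore cannot tell what power the trial has for its primary analysis.

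The answer depends on the contrast, which the plan leaves open. Some reasonable contrasts have ample power at 150 and others fall short of 80%. An unnamed contrast can also be chosen after the data are seen. The same three-assessment count is carried over to secondary outcomes, where the schedule does not deliver it for all of them.

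**Working it through.** **Inputs.** From Sample Size: d = 0.5 SD, correlation ρ = 0.4, 80% power, alpha 0.05, 10% dropout. From Randomization and Description of Study Population: 2:1 and 150. Assumptions: two-sided alpha, the same correlation between every pair of visits, 0.5 SD at each post-workshop visit, all 150 randomised, no clustering within workshops. Then 100:50 less 10% is 90:45.

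**The plan's own figure.** For a time-averaged difference with m assessments and equal groups:

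n = 2(1.96 + 0.8416)² × [1 + (m − 1)ρ] / (m d²) = 2 × 7.849 × 1.8 / (3 × 0.25) = 37.67, so 38.

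38/0.9 = 42.2, so 43. One-sided alpha gives 29.7 and does not reproduce the figure. The plan's arithmetic is right; its inputs are those of another design.

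**Power for the planned design.** Power = Φ(d / √[v(1/n₁ + 1/n₂)] − 1.96), where v is the variance of the contrast in SD² units. At 90:45, 1/90 + 1/45 = 1/30.

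| Contrast | v | Power, 90:45 | Power, 38:38 |
|---|---|---|---|
| Plan's formula (0.5 SD at all three) | 1.8/3 = 0.60 | 94% | 80% |
| Mean of weeks 6 and 12, baseline-adjusted | 0.70 − 0.16 = 0.54 | 96% | 84% |
| Mean of weeks 6 and 12, baseline unused | 1.4/2 = 0.70 | 91% | 74% |
| Week 12, baseline-adjusted | 1 − 0.16 = 0.84 | 85% | 66% |
| Average change from baseline | 0.70 + 1 − 0.80 = 0.90 | 82% | 63% |
| Raw week-12 change | 2(1 − 0.4) = 1.20 | 71% | 51% |
| Group main effect over three visits | 0.60, with d = 0.5 × 2/3 | 65% | 47% |

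For the 2-df group-by-time test with categorical time, the two changes from baseline each have variance 1.2 and covariance 0.6. The noncentrality at 90:45 is 0.25 × 2/(1.2 + 0.6) × 30 = 8.33, which gives 74%.

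**Number to randomise at 2:1 for 80% power.** Total = 4.5 v × 7.849 / d² / 0.9:

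- baseline-adjusted mean: 84.8, about 85
- baseline-adjusted week 12: 131.9, about 132
- average change: 141.3, about 142
- raw week-12 change: 188.4, about 189

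For week 12 it therefore matters whether 150 counts people enrolled or people randomised.

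**Secondary outcomes with one follow-up (such as PWV), 90:45.** At 0.5 SD: 71% (raw change, v = 1.20) to 85% (baseline-adjusted, v = 0.84). At 0.66 SD, the size that Sample Size discusses for flow-mediated dilation: 0.66/√(1.20/30) − 1.96 = 1.34, or 91%; 0.66/√(0.84/30) − 1.96 = 1.98, or 98%. For retinal measures no power for change can be computed, because no follow-up imaging is scheduled.

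**The case against.** The strongest reply is that no shortfall has been shown, and that stands. Forty-three per group is a minimum, and 100:50 exceeds it in both arms. The plan's own formula gives 94% at 90:45. Even 38 per group gives 84% for the baseline-adjusted follow-up mean. A reader might infer that the trial is underpowered; the documents do not support that.

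A reader might also take 65% as the trial's power. That figure needs a group main effect averaged over baseline as well as follow-up. Primary Endpoint Analysis opens by speaking of changes in anxiety and allows a random slope, so time is in view, and a main effect of this kind does not test change. It is a literal reading, but a weak one. Likewise 189 is the requirement for raw week-12 change only; average change, also without baseline adjustment, needs about 142, which is below 150.

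The baseline is less open than two pre-workshop inventories suggest. Visit 1 is titled as consent and screening, Visit 2 as the pre-intervention visit, and Visit 4 as the second experimental visit. Visit 2 is the natural baseline; the plan need only say so.

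On vascular outcomes, a wrong assessment count does not by itself defeat the power claim: PWV keeps 91–98% at 0.66 SD. The missing retinal follow-up may be a slip in the schedule, since Research Question and Hypothesis predicts a retinal improvement and Purpose says vascular assessments are repeated.

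What remains is that the stated size and power do not describe this trial, and that power cannot be stated until the contrast is named.

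**Conclusion.** The point holds as a mismatch between the sample size calculation and the design, and it should be fixed. The stated 38/43 per group and 80% assume equal groups and a treatment difference at baseline. For the planned trial, power on contrasts that use post-workshop data sensibly runs from 71% (raw week-12 change) to 96% (baseline-adjusted follow-up mean), with 85%, 82% and 74% for the other contrasts that use baseline.

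These figures rest on the plan's 0.5 SD and correlation 0.4, two-sided 0.05, equal correlation between visits, all 150 randomised, 10% dropout and no workshop clustering. The documents give no intraclass correlation, so no clustered figure is offered as a finding. That the formula assumes a difference at all three assessments is inferred from its reproducing 38.

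The three-assessment basis is wrong for PWV, and for retinal imaging as scheduled. The first leaves 71–85% at 0.5 SD; the second leaves nothing to power until the schedule is reconciled.

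**What to change.** 1. In Primary Endpoint Analysis, name the contrast. For example: the primary contrast is the ACT–control difference in the mean of the 6- and 12-week BAI (or at week 12), adjusted for baseline, from a mixed model with group-by-time terms and baseline means constrained equal; baseline is the Visit 2 inventory. This keeps baseline among the repeated responses, as the plan already has it.

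2. In Sample Size, replace the 38/43 calculation. For example: with 150 randomised 2:1 and 10% dropout (90:45), correlation 0.4 and two-sided alpha 0.05, power to detect 0.5 SD in this contrast is 96% (week 12: 85%), without allowance for clustering within workshops. State whether 150 is enrolled or randomised, and recompute if fewer will be randomised. If clustering is shown, label the intraclass correlation as an assumption and state the variance to which it applies.

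3. Restate secondary power by the number of post-treatment measurements each outcome has. Reconcile the Visit 1-only retinal schedule with Purpose, Research Question and Hypothesis, and Sample Size; withdraw the retinal power claim if there is no follow-up imaging. Reconcile the statement in Secondary Endpoint Analysis that physiological variables have two time points, and the timing in Purpose, with the 6-week forearm flow and mSNA measurements.

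The cost is a rewritten Sample Size paragraph, a few sentences in the analysis section and consistent schedule wording. With a baseline-adjusted contrast, all 150 randomised and no clustering, no extra participants are needed on the plan's inputs.

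### The power stated for secondary outcomes assumes three assessments, but pulse wave velocity, carotid compliance and 24-hour pressure have two and retinal imaging is listed once; flow-mediated dilation, the clinical yardstick, is not measured.

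*Combined protocol and SAP*

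**What the plan says.** The Sample Size section of the combined protocol and SAP sets up one calculation, "based on three assessments for primary and secondary outcomes", with "a correlation of outcome measures over the duration of the study within individuals of 0.4". Its result is that "a total of 38 participants are needed per group to detect an effect size of 0.5 SD with 80% power", raised to 43 per group for 10% dropout. It then extends the claim: "Similarly, we are powered to detect clinically significant effects for the secondary outcomes of vascular function". The support is a cohort finding that "a reduction in FMD of 0.66 SD was associated with a 30% increased risk of cardiovascular events" and a second cohort result on the same 0.66 SD scale. The vascular measures it names are pulse wave velocity, forearm blood flow and retinal microvascular measures.

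The Secondary Endpoint Analysis section says linear regression is enough for relating physiological variables to change in anxiety, "since these physiological variables are only measured at two points". For the group comparison of these outcomes it refers back to the primary mixed model. The Purpose section places vascular function at baseline and 12 weeks.

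The Assessment Schedule, which the control group follows apart from the workshop, gives different counts by outcome:

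- STAI: baseline, 6 weeks and 12 weeks, so at least three.
- Forearm blood flow (venous occlusion plethysmography) and mSNA: Visit 2, the 6-week visit and Visit 4, so three.
- Pulse wave velocity, carotid compliance and 24-hour pressure: Visits 2 and 4, so two.
- Retinal imaging: Visit 1 only. Visit 4 is defined as a repeat of Visit 2, which contains no retinal testing.

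**The concern.** One assessment count is used for every secondary outcome, and it is wrong for several of them. A two-visit outcome has a single post-intervention value, so its treatment contrast is less precise than an average over three occasions, and the stated 80% at 0.5 SD does not carry over. An outcome with no scheduled post-intervention value has no treatment contrast at all.

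The clinical yardstick does not help. A risk association per 0.66 SD of brachial FMD says nothing about how large a change in pulse wave velocity, forearm flow or retinal flow would matter, and no FMD procedure is described. The only brachial ultrasound is an optional flow measurement during microneurography.

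At stake is the reading of a null result. If pulse wave velocity shows no difference, the Sample Size text invites the conclusion that a clinically important effect was ruled out with 80% power, which the calculation does not support.

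**Working it through.** **Inputs.** From Sample Size: effect 0.5 SD, correlation ρ = 0.4, α = 0.05, power 80%, 38 per group, 10% dropout, vascular yardstick 0.66 SD. From Randomization: 2:1. From Description of Study Population: 150 enrolled. Sidedness is not stated; two-sided is used because it reproduces 38, whereas one-sided gives 30.

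**Plan's figure.** For the difference in means averaged over m occasions, n per group = 2(1.960 + 0.842)²[1 + (m − 1)ρ] / (m d²). With m = 3: 2 × 7.849 × 1.8 / (3 × 0.25) = 37.7, so 38. Then 38/0.9 = 42.2, so 43. Both stated figures reproduce.

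**Two-visit outcomes.** The variance factor V, in units of the outcome variance, depends on the analysis:

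- Plan's formula with m = 2: V = (1 + 0.4)/2 = 0.70.
- Baseline-adjusted follow-up: V = 1 − 0.4² = 0.84.
- Change score: V = 2(1 − 0.4) = 1.20.

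SE = √[V(1/n₁ + 1/n₂)], power = Φ(d/SE − 1.96), and the difference detectable with 80% power = 2.80 × SE.

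| Numbers analysed | Method | SE | Power at 0.5 SD | Power at 0.66 SD | Detectable difference |
|---|---|---|---|---|---|
| 38:38 | plan's formula, m = 2 | 0.192 | 74% | 93% | 0.54 SD |
| 38:38 | baseline-adjusted | 0.210 | 66% | 88% | 0.59 SD |
| 38:38 | change score | 0.251 | 51% | 75% | 0.70 SD |
| 90:45 | plan's formula, m = 2 | 0.153 | 91% | 99% | 0.43 SD |
| 90:45 | baseline-adjusted | 0.167 | 85% | 98% | 0.47 SD |
| 90:45 | change score | 0.200 | 70% | 91% | 0.56 SD |

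The 90:45 split is 150 × 0.9 = 135 divided 2:1. It assumes that everyone enrolled is randomized, which the documents do not say; consent comes before screening.

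The m = 2 row averages baseline with follow-up as if both carried the treatment effect. Baseline precedes the intervention, so the other two rows are the relevant ones for a single post-intervention value.

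**Sensitivity to the correlation.** The documents give no correlation specific to vascular measures. Power at 0.5 SD for ρ from 0.2 to 0.8:

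- 38:38: 60% to 95% baseline-adjusted; 41% to 93% change score.
- 90:45: 80% to over 99% baseline-adjusted; 58% to 99% change score.

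The baseline-adjusted detectable difference runs from 0.63 down to 0.39 SD at 38:38, and from 0.50 down to 0.31 SD at 90:45.

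**Three-assessment outcomes.** For forearm flow and mSNA, the baseline-adjusted mean of the 6- and 12-week values has V = (1 + 0.4)/2 − 0.4² = 0.54, and 38 per group gives 84% at 0.5 SD. The plan's claim is reasonable for these at ρ = 0.4.

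**Retinal imaging.** With one pre-intervention measurement scheduled, no power for a treatment effect can be computed.

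**The case against.** The arithmetic of 38 and 43 is correct, and the three-assessment structure does fit some secondary outcomes: both STAI subscales, forearm flow and mSNA. Forearm flow is a named prediction of the trial. That stands, so striking secondary outcomes from the calculation altogether would introduce a new error. It also means that the two-point statement in Secondary Endpoint Analysis conflicts with the 6-week schedule for forearm flow and mSNA.

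The drop from 80% to 51% combines a change in the number of assessments with a change of method. Holding the plan's formula fixed, the drop is only to 74%, and a change score would give just 63% even with three assessments (V = 0.90). That stands against the change-score figure but not against the baseline-adjusted 66%.

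A reader might infer that the trial is underpowered for vascular outcomes. The documents do not support that. Enrolment of 150 exceeds the 2 × 43 = 86 that the calculation requires. At 0.66 SD, 38 per group still gives 88% with baseline adjustment, and only the change score (75%) falls below 80%. These outcomes are also described as exploratory, which limits the harm. None of this rescues the stated derivation, or the use of FMD as a yardstick for measures other than FMD.

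**Conclusion.** The concern holds as a fault in the power statement. For pulse wave velocity, carotid compliance and 24-hour pressure, the calculation given does not deliver 80% power at 0.5 SD with 38 per group. At correlation 0.4, two-sided 0.05, it delivers 66% with baseline adjustment or 51% with change scores, and the detectable difference is 0.59 or 0.70 SD. With 90:45 analysed, power is 85% or 70% and the detectable difference 0.47 or 0.56 SD. Adequate power is therefore undemonstrated, not shown to be missing.

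These figures rest on two assumptions: that 0.4 applies to vascular measures and, for 90:45, that all 150 are randomized. They do not apply to forearm flow or mSNA, which have three assessments, or to retinal measures, which have no scheduled post-intervention value. The FMD associations define no clinically significant difference for any vascular outcome named in Sample Size.

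**What to change.** 1. In Sample Size, limit the three-assessment statement to the outcomes that have three assessments.
2. For the two-visit outcomes, state the detectable difference using the 2:1 ratio. Label the correlation of 0.4 and the number randomized as assumptions, and give a range over both.
3. In Secondary Endpoint Analysis, prespecify baseline adjustment for the two-visit outcomes. At correlation 0.4 and 0.5 SD this choice is worth about 15 percentage points of power (66% against 51%, or 85% against 70%).
4. Remove the conclusion drawn from FMD.
5. Reconcile Purpose, Assessment Schedule, Secondary Endpoint Analysis and Sample Size on how often forearm flow, mSNA and retinal measures are taken. Make no power claim for retinal measures unless a post-intervention measurement is scheduled.

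The cost is text changes in these sections and a less favourable stated figure for the two-visit outcomes. No more participants are needed.
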